#### 8.2.2. Other Secondary Endpoints - Categorical

The ICE strategy for the Key Secondary Estimand described in Section 8.2.1.1 above will be replicated in the following secondary Efficacy endpoints:

Endpoint	Endpoint name to be displayed for Estimand Analysis
Adapted Mayo Clinical Remission at Week 10	Secondary – Adapted Mayo Clinical Remission
Adapted Mayo Clinical Response at Week 10	Secondary – Adapted Mayo Clinical Response
Symptomatic Remission at Week 10	Secondary – Symptomatic Remission

The “Secondary Estimand – Clinical Remission” will be analysed by replicating the statistical model described in Section 8.2.1.2 above. The other two estimands in the table above will be summarised only.

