#### **2.1.4. Changes to Efficacy Estimands and Statistical Analyses**

The “Hypothetical” additional estimand for Complete Mayo Score has been removed to simplify the reporting of efficacy.

The primary estimand (Complete Mayo Score) and key secondary estimand (Endoscopic Improvement) have been modified to account for “discontinuation due to sponsor’s decision to terminate the study” intercurrent event.

New estimands are defined for secondary continuous and categorical efficacy endpoints. The populations and intercurrent event strategies for these estimand are the same as the Primary estimand for Complete Mayo Score (in the case of secondary continuous endpoints) or Key secondary estimand for Endoscopic Improvement (in the case of secondary categorical endpoints).

The primary dose response model for Complete Mayo Score has been modified to only analyse the 450mg IV and Placebo IV arms due to projected lack of patients randomised to other treatment arms following study termination.

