**Footnotes:**

[figure not shown]
- 1 Potential clinical importance is defined in Section 15.8 for each relevant safety endpoint.
- 2 The Complete 4-domain Mayo score is used for the primary endpoint due to its wider dynamic range for assessment of dose-response compared to the Adapted Mayo score used for secondary and exploratory endpoints.
- 3 Clinical response and remission for the various iterations of Mayo score are defined in [Appendix 7](#), Section 15.7.
- 4 Symptomatic remission is defined as a rectal bleeding subscore of 0, and a stool frequency subscore of  $\leq 1$ , with no worsening from baseline.
- 5 Taper period is defined from the start of the taper (Weeks 12 or 24, respectively, for the Double-Blind and Open Label Extended Treatment Phases) to completion of the respective Extended Treatment Phases.

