## 8.2. Secondary Efficacy Analyses

### 8.2.1. Key Secondary Endpoint

#### 8.2.1.1. Estimand

Key secondary estimand for decision making: "Composite"	
Objective:	To investigate the effect of repeat doses of GSK2831781 on clinical efficacy including endoscopic mucosal healing during the Double-Blind Induction Phase.
Estimand:	
Description
 
Difference in response rates between active doses of GSK2831781 and Placebo when added to background therapy in patients with moderate to severe, active Ulcerative Colitis.
 
Attributes
 
 
• Treatment: Placebo and active doses of GSK2831781 in addition to background therapy and stable dose of corticosteroid where relevant.
 
• Population: Patients with moderate to severe, active, Ulcerative Colitis as per inclusion/exclusion criteria.
 
• Outcome measure: Endoscopic Mucosal Healing at Week 10 assessment, where success is defined as: 
 
○ Achieving a score on the endoscopic component of the Adapted Mayo score of 0 or 1, and
 
○ Not discontinuing IP due to reasons unrelated to the COVID-19 pandemic or to sponsor's decision to terminate the study, and
 
○ Not taking medications excluded by the protocol or increasing dose of corticosteroid.
 
 
 
• Intercurrent events and strategy: 
 
○ ICE: discontinuation from IP, unrelated to COVID-19 pandemic or to sponsor's decision to terminate the study.
 
○ Strategy: included in outcome via composite strategy (i.e. post-ICE result set to non-response).
 
○ ICE: discontinuation from IP, due to COVID-19 pandemic.
 
○ Strategy: hypothetical, setting response status to missing.
 
○ ICE: discontinuation from IP, due to sponsor's decision to terminate the study.
 
○ Strategy: hypothetical, setting response status to missing.
 
○ ICE: valid endoscopy result not available, due to COVID-19 pandemic
 
 
 

Key secondary estimand for decision making: “Composite”	

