	
 
○ Strategy: hypothetical, setting response status to missing.
 
○ ICE: valid endoscopy result not available, for technical reasons
 
○ Strategy: hypothetical, setting response status to missing.
 
○ ICE: prohibited medication taken
 
○ Strategy: included in outcome via composite strategy (i.e. post-ICE result set to non-response).
 
○ ICE: increase in dose of permitted medications
 
○ Strategy: included in outcome via composite strategy (i.e. post-ICE result set to non-response).
 
● Population-level summary: Difference in proportion of participants who achieve response between placebo and relevant active doses
 

Estimation and missing data details for the key secondary estimand for decision making (“Composite”)	
	
Participants who have a missing assessment at Week 10 for reasons unrelated to the COVID-19 pandemic will be counted as non-responders in the analysis.
 
The ICEs that will be dealt with using a hypothetical strategy will have response status set to missing
 
In all cases, the missing response status will be assumed to be MAR in the statistical analysis.
 
The MAR assumption is implicit in the planned Bayesian analysis.

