### **15.6.3. Efficacy**

#### **15.6.3.1. Mayo score versions**

All Mayo scores are the sum of the components. The number of components and their definition vary as described below and will be derived programmatically. Stool Frequency and Rectal Bleeding will be derived from eDiary data.

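### Symptomatic Remission is scored from the diary alone, but SAP 8.2.2 applies to it the endoscopy-unavailable intercurrent events, so in two situations an observed Week 10 outcome drops out of the estimand summary

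*SAP*

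**What the plan says.** SAP Section 8.2.2 defines the estimands for the other categorical secondary endpoints by reference: "The ICE strategy for the Key Secondary Estimand described in Section 8.2.1.1 above will be replicated in the following secondary Efficacy endpoints". The table below that sentence names Adapted Mayo Clinical Remission, Adapted Mayo Clinical Response and Symptomatic Remission, all at Week 10. Section 2.1.4 gives the same rule, matching populations and event strategies to the "Key secondary estimand for Endoscopic Improvement (in the case of secondary categorical endpoints"). Neither place makes an exception.

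The strategy being copied is in Section 8.2.1.1. Two of its events concern the endoscopy itself: "ICE: valid endoscopy result not available, due to COVID-19 pandemic" and "ICE: valid endoscopy result not available, for technical reasons". Each carries the instruction "Strategy: hypothetical, setting response status to missing". The missing-data notes in the same section add: "Participants who have a missing assessment at Week 10 for reasons unrelated to the COVID-19 pandemic will be counted as non-responders in the analysis".

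The endpoint is defined in footnote 4 to SAP Section 2.2: "Symptomatic remission is defined as a rectal bleeding subscore of 0, and a stool frequency subscore of" 1 or less, without worsening from baseline. Section 15.6.3.1 gives the source of both components: "Stool Frequency and Rectal Bleeding will be derived from eDiary data".

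**The concern.** Clinical remission and response on the Adapted Mayo score cannot be computed without an endoscopic sub-score, so an event for an unavailable endoscopy makes sense there. Symptomatic Remission needs no endoscopy. A participant with a usable diary at Week 10 whose sigmoidoscopy was cancelled because of the pandemic, or could not be read, has a fully observed outcome. The copied rule nevertheless sets that outcome to missing.

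The situation is foreseeable. The diary is completed daily at home (Protocol Section 8.2.4.1), whereas endoscopy visits are excluded from home healthcare (Protocol Appendix 10). A lost endoscopy alongside an intact diary is a natural pattern in the pandemic.

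At stake are real data on a declared secondary endpoint. A reader would also find that the observed summary (Table 2.17) and the estimand summary (Table 2.28) differ for a reason that has nothing to do with the endpoint.

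**Working it through.** There is no figure in the plan to reproduce. The check is textual, followed by an illustration on assumed inputs.

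**Step 1. Does the endpoint use endoscopy?** No. SAP Sections 2.2 (footnote 4) and 15.6.3.1 define it from two eDiary sub-scores. The protocol lists it as an over-time endpoint, and the Schedule of Activities has no endoscopy at Weeks 2, 4 or 6, so the plan already treats it as measurable without one.

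**Step 2. Does the rule reach it?** Yes. Sections 2.1.4 and 8.2.2 both carry the full strategy across. Section 15.6.3.5 gives a single event order for the secondary estimand, and that order includes the unavailable endoscopy. Table 2.28 has no endpoint list of its own; that it covers Symptomatic Remission is inferred from Section 8.2.2.

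**Step 3. Which participants are affected?** Reading Section 8.2.1.1 for a participant with a usable Week 10 diary and no valid endoscopy:

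| Situation | Status under the copied rule |
|---|---|
| Endoscopy unavailable, COVID-19 | Missing |
| Endoscopy unavailable, technical | Missing under the event; non-response if the missing-data note is applied |
| Earlier discontinuation of study drug, unrelated to COVID-19 or study termination | Non-response (composite) |
| Earlier prohibited medication or dose increase | Non-response (composite) |

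Only the first two rows are at issue. In the second row the section is inconsistent: a technical failure is both a named event set to missing and a reason unrelated to COVID-19.

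**Step 4. How is comparable data treated elsewhere?** Section 8.2.3 gives Partial Mayo, which uses the same two diary items plus the physician's assessment, the strategy of the primary estimand (Section 8.1.1.1). That strategy has discontinuation events only. The same participant's Week 10 diary is kept for Partial Mayo and dropped for Symptomatic Remission.

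**Step 5. Illustration.** All three inputs are assumptions: true remission p = 25%, share removed m = 5%, 10% or 15%, remission among those removed r = 40%, 25% or 15%. If they are set to missing, the reported rate is (p - m x r)/(1 - m).

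| m | r = 40% | r = 25% | r = 15% |
|---|---|---|---|
| 5% | (0.25 - 0.020)/0.95 = 24.2% | 25% | (0.25 - 0.0075)/0.95 = 25.5% |
| 10% | (0.25 - 0.040)/0.90 = 23.3% | 25% | (0.25 - 0.0150)/0.90 = 26.1% |
| 15% | (0.25 - 0.060)/0.85 = 22.4% | 25% | (0.25 - 0.0225)/0.85 = 26.8% |

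The standard error grows by 1/sqrt(1 - m): 1.026, 1.054 and 1.085.

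For scale, take the arms of 40 and 20 planned for Interim Analysis 3 (Protocol Section 9.2.1). The binomial standard error at 25% is sqrt(0.25 x 0.75/40) = 6.8 points and sqrt(0.25 x 0.75/20) = 9.7 points. The largest shift above, 25 - 22.4 = 2.6 points, is 2.6/6.8 = 0.38 and 2.6/9.7 = 0.27 of a standard error.

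If technical failures were instead counted as non-response, and all of the share m were of that kind, the rate would be p - m x r. With r = 25% that is 0.25 - 0.05 x 0.25 = 23.75%, 0.25 - 0.10 x 0.25 = 22.5% and 0.25 - 0.15 x 0.25 = 21.25%. Under that reading the rate can only be lowered.

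**The case against.** The case for leaving the text alone is mostly about consequence, and much of it stands. Section 8.2.2 says this estimand is summarised only: no model is fitted and no success rule uses it. The decision criteria rest on endoscopic healing (Protocol Sections 9.2.1 and 9.4.1). Table 2.17 reports Symptomatic Remission as observed and is a final deliverable, and diary data also appear in the daily diary summaries and the Partial Mayo analysis. Nothing is lost from reporting as a whole.

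Three stronger readings are tempting and are not supported.

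- A reader might infer that every participant without a Week 10 endoscopy is lost. Only two causes lead to missing; discontinuation for other reasons and prohibited medication give non-response.
- A reader might infer a bias because patients who feel well or unwell skip the endoscopy. That describes patient choice, which is not one of the two events. Nothing in the documents ties a pandemic cancellation or an unreadable recording to symptoms.
- A reader might infer that the result rests on a missing-at-random model. None is fitted to this endpoint; those set to missing simply leave the proportion.

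None of this supplies a reason for applying an endoscopy event to a diary endpoint. In the protocol (Section 3) these events belong only to the endoscopic healing estimand, and the SAP gives no rationale for extending them here.

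**Conclusion.** The rule is wrong as written. Taken literally, it removes an observed diary outcome from Table 2.28 when a valid endoscopy is unavailable because of COVID-19 or for technical reasons. For technical failures, Section 8.2.1.1 also allows a reading as non-response.

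The effect is probably small and consists mainly of lost data, an unexplained difference between Tables 2.17 and 2.28, and an inconsistency with Partial Mayo. The size cannot be fixed from the documents, which give neither a rate of missing endoscopy nor a remission rate among those affected. If those removed resemble those kept within each arm, there is no bias and only precision is lost. The shifts in the illustration depend entirely on the assumed remission rates. This is a correction worth making to a descriptive secondary endpoint; it does not threaten the trial's conclusions.

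**What to change.** 1. In SAP Section 8.2.2, state that for Symptomatic Remission the two events for an unavailable valid endoscopy do not apply, that status is derived from the eDiary sub-scores whenever these are available, and that all other events are handled as in Section 8.2.1.1.
2. Make the same exception in the event order in Section 15.6.3.5. As it stands, an unavailable endoscopy ranks above excluded medication when both fall at the same timepoint. If that order also governs the imputation, a composite failure could become missing for an endpoint that never needed endoscopy.
3. State that, for this endpoint, the Section 8.2.1.1 rule counting missing Week 10 assessments as non-response refers to missing diary sub-scores and not to a missing endoscopy.

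The cost is a few lines of SAP text and a small programming change. No new data are needed.

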### 8.2.3. Other Secondary Endpoints - Continuous

The ICE strategy for the Primary Estimand described in Section 8.1.1.1 above will be replicated in the following secondary Efficacy endpoints:

Endpoint	Endpoint name to be displayed for Estimand Analysis
Change from Baseline in Partial Mayo Score at Weeks 2, 4, 6, 10	Secondary – Partial Mayo Score
Change from Baseline in Adapted Mayo Score at Week 10	Secondary – Adapted Mayo Score
Change from Baseline in Adapted Mayo endoscopic score at Week 10	Secondary – Endoscopic Score
Change from Baseline in UCEIS at Week 10	Secondary – UCEIS Total Score

The four estimands in the table above will be summarised in tables.

In addition, a Bayesian repeated measures analysis will be conducted for the Partial Mayo score, the estimand is described below and the analysis details below that.

#### 8.2.3.1. Statistical Analysis

Bayesian Repeated Measures Analysis for Continuous Endpoint	
Endpoint	Change from baseline in Partial Mayo Score
Statistical analysis	GLMM with natural link (equivalent to MMRM)
Model	$\mathbf{y}_i \sim \text{Normal}(\boldsymbol{\mu}_i, \sigma^2 \mathbf{I}_J)$ $\boldsymbol{\mu}_i = \mathbf{X}_i \boldsymbol{\beta} + \mathbf{Z}_i \mathbf{b}_i$
Outcome	$\mathbf{y}_i$ = vector of change from baseline values for participant $i$
Prior for $\sigma$	$\sigma$ = between-participant SD, $\sim \text{Gamma}\left(2, \frac{1}{A}\right)$ with A reasonably large e.g. A=10 (Chung, 2013)
Population-level coefficients ( $\boldsymbol{\beta}$ )	
 
<math>\boldsymbol{\beta}</math> = fixed effects, parameters associated to predictors  <math>\beta_0</math> = intercept, two possible prior distributions*:  Vague: <math>\text{Normal}(0, sd = 100)</math>  Weakly informative: see Appendix 14: Details of the Informative Placebo Prior  <math>\beta_k \sim \text{Normal}(0, sd = 100)</math>
 

Bayesian Repeated Measures Analysis for Continuous Endpoint	
Predictors ( X )	
 
• TRT = study treatment(categorical)
 
• visit = visit (categorical)
 
• TRT*visit = study treatment by-visit interactions (categorical)
 
• BASE = baseline value of dependent variable (continuous) 
 
• Partial Mayo Score
 
 
 
• BASE*visit =baseline value by-visit interactions (continuous)
 
• Advanced therapy experience (categorical stratification variable)
 

Random effects ( b )	
 
• <math>Z_i</math> = known design matrix for the random effects
 
• <math>b_i</math> = unknown subject-level random effects, <math>\sim \text{Normal}(0, \Sigma_b)</math>, where <math>\Sigma_b</math> within-subject covariance matrix
 
• <math>\Sigma_b \sim \text{Inverse Wishart}(J, S)</math>, with <math>J</math> = number of visits (degree of freedom), <math>S</math> = covariance matrix (identity matrix)
 

\* The parameterisation of the priors used in the analysis will be reported in the clinical study report.

The details of the scores and indexes including the Complete, Partial and Adapted Mayo scores, and the corresponding definition of response and remission are described in Section 15.6 Appendix 6: Derived and Transformed Data.

Note that the absolute values for each endpoint listed as change from baseline will also be reported for each timepoint.

### 8.3. Exploratory Efficacy Analyses

Exploratory efficacy endpoints include the primary and secondary endpoints in the post-induction study phases (ETP, OL, OL ETP). Unless stated otherwise, exploratory efficacy endpoints will be listed but not summarised.

## **9. PATIENT REPORTED OUTCOMES ANALYSES**

Exploratory Patient reported outcomes (PROs) are not covered by this RAP.

## 10. PHARMACODYNAMIC AND BIOMARKER ANALYSES

### 10.1. Pharmacodynamic and Biomarker Analyses

Details of the planned displays are provided in [Appendix 12](#): List of Data Displays and will be based on GSK Data Standards and statistical principles.

Biomarker endpoints will be summarised in Double Blind Induction by treatment using descriptive statistics, graphically presented and listed. Figures summarising these endpoints will show Geometric Mean with 95% CI.

#### 10.1.1. Endpoint / Variables

- Serum C-reactive protein over time in participants with elevated CRP at baseline (e.g. CRP  $\geq 5$  mg/L)
- Faecal calprotectin over time
- Absolute and ratio to baseline in number of CD3 and LAG3 cells by Immunofluorescence (IF) in colon biopsies taken in two tissue types (Lamina Propria or Crypt/Epithelium) for the following derived parameters:

Description	Name in outputs (superscript not available)	Units for derived variables
% CD3 negative and Lag3 positive from total Lag3 positive cell population (% Lag3 positive non-T cells)	CD3-LAG3+ as % of Total LAG3+	%
% CD3 positive and Lag3 positive from total Lag3 positive cell population (% Lag3 positive T cells)	CD3+LAG3+ as % of Total LAG3+	%
CD3 positive cells per mm  tissue	CD3+	cells/mm 
Lag3 positive cells per mm  tissue	LAG3+	cells/mm 
CD3 positive and Lag3 negative cells per mm  tissue	CD3+LAG3-	cells/mm 
CD3 negative and Lag3 positive cells per mm  tissue	CD3-LAG3+	cells/mm 
CD3 positive and Lag3 positive cells per mm  tissue	CD3+LAG3+	cells/mm 
CD3 + LAG3 + cells/mm  in Lamina Propria are the primary biopsy endpoint (also referred to as mucosal CD3+LAG3+ cell count ) and will also be a potential covariate for efficacy and biomarker analysis.		

- Ratio to baseline in the following cell types from flow cytometry. The table below shows the cell description and the endpoint name shown in outputs for flow cytometry data.

Description	Name in outputs (superscript not available)
J11L1 + memory T helper cells	CD3+CD4+CD45RA-J11L1+
REA351 + memory T helper cells	CD3+CD4+CD45RA-REA351+
J11L1 + memory CD4  T cells	CD3+CD4-CD45RA-J11L1+
REA351 + memory CD4  T cells	CD3+CD4-CD45RA- REA351+
Note: REA351+ represents cell depletion, J11L1+ represents receptor occupancy.	

## 11. PHARMACOKINETIC ANALYSES

The purpose of the pharmacokinetic analysis is to characterize the PK after repeat IV and subcutaneous dosing of GSK2831781.

### 11.1. Pharmacokinetic Analyses

#### 11.1.1. Endpoint / Variables

- AUC(0-tau)
- Cmax
- tmax
- PK concentration
- Soluble LAG3 (sLAG3) concentration

##### 11.1.1.1. Drug Concentration Measures

Refer to [Appendix 5](#): Data Display Standards & Handling Conventions (Section 15.5.3 Reporting Standards for Pharmacokinetic)

##### 11.1.1.2. Derived Pharmacokinetic Parameters

Pharmacokinetic parameters will be calculated by standard non-compartmental analysis of PK concentration according to current working practices and using the currently supported version of WinNonlin (version 6.3 or higher). All calculations of non-compartmental parameters will be based on actual sampling times. Pharmacokinetic parameters listed will be determined from the plasma concentration-time data, as data permits.

Parameter	Parameter Description
AUC(0-tau)	Area under the concentration curve to the end of the dosing period
Cmax	Maximum concentration observed
tmax	Time at which the maximum concentration Cmax is observed

##### NOTES:

- Additional parameters may be included as required.

#### 11.1.2. Summary Measure

- All endpoints/variables defined in Section 11.1.1 will be summarized by treatment over time using descriptive statistics, graphically presented (PK and sLAG3 concentrations) and listed.

#### 11.1.3. Population of Interest

The pharmacokinetic analyses will be based on the “Pharmacokinetic” population, unless otherwise specified.

#### 11.1.4. Statistical Analyses / Methods

Details of the planned displays are provided in [Appendix 12](#): List of Data Displays and will be based on GSK Data Standards and statistical principles.

Descriptive statistics (e.g., n, arithmetic mean and corresponding 95% confidence interval, standard deviation, minimum, median, maximum, CVb%) will be calculated for all pharmacokinetic endpoints by treatment. For tmax, CVb% will be calculated for each treatment as:  $CVb\% = 100 \times (\text{SD}/\text{mean})$ , where SD and mean are the standard deviation and mean of the untransformed data. For AUC(0-tau) and Cmax, geometric means and between subject CVs will be calculated for each treatment as:

Geometric mean =  $\exp(\text{mean on loge scale})$

$CVb(\%) = \sqrt{\exp(\text{SD}^2) - 1} \times 100$ ,

where SD is the standard deviation of the loge transformed data.

## 12. POPULATION PHARMACOKINETIC (POPPK) ANALYSES

The primary goal of this analysis is to characterize the population pharmacokinetics of GSK2831781 following repeat intravenous and subcutaneous dosing in participants with active ulcerative colitis. The influence of participant demographics, baseline characteristics, including disease activity, and impact of anti-drug antibodies on the pharmacokinetics of GSK2831781 in this population will be investigated. The individual participant PK parameters will be estimated and documented for the purposes of any subsequent exposure-response (PK/PD) analyses.

### 12.1. Statistical Analyses / Methods

A summary of the planned population pharmacokinetic analyses is outlined below:

- Drug GSK2831781 concentration-time data will be subjected to nonlinear mixed effects modelling using the program NONMEM to develop a population PK model.
- To support this analysis a PopPK dataset will be generated. The details for the dataset specifications are provided in a separate document.

Detailed PopPK methodology is presented in [Appendix 9: Population Pharmacokinetic \(PopPK\) Analyses](#).

A population PK report will be produced by CPMS and presented separately from the main clinical study report (e.g. as an appendix).

